#### ***10.4. Interim Analysis and Study Monitoring***

NICHHD will determine the members of the DSMB that will be responsible for monitoring the project.

#### ***10.5. Analysis of Primary and Secondary Hypotheses***

At the group level, the primary outcome variable is the percentage of primary and secondary outcomes during the three months following the end of the intervention. Despite having only 12 observations in each arm, since each percentage is based on a large number of births, one can use the Normal approximation to the Binomial distribution, and thus the individual percentages can be assumed to be Normally distributed. This implies that when evaluating the efficacy of the intervention using the mean percentages at the end of the intervention period, the Student's t-test is appropriate and its use is justified. Baseline frequencies will also be presented, and baseline to follow-up ratios will be computed. Mantel Haenszel summary risk ratios combining the individual ratios for each hospital in the intervention group and non-intervention group will be computed. The intervention and non-intervention groups will then be compared at the group level using Student's t-test on the logarithms of the summary risk ratio (Wyatt et al., 1998).

In addition, the data collected at the individual level will be used to explore the potential for confounding of the main effects of the intervention due to imbalances arising from the group randomization. Such multi-level analyses will use mixed model techniques (Littell et al., 1996), also known as hierarchical linear models (Bryk and Raudenbush, 1992). These models account for the clustering effect and the intra-hospital correlation of the women from a given hospital. Furthermore, we will use descriptive statistics and GEE modeling (Diggle et al., 1994) to study the evolution of frequencies of outcomes between the four data collection periods.

For the analysis of provider's "readiness to change", the analysis will include three variables, one assessing "readiness to change" episiotomy, one assessing "readiness to change" management of third stage of labor and one assessing attitude toward changing practice in general. Ordinal scales will be used for the responses. Data will be summarized in terms of medians and interquartile ranges. Non-parametric statistics will be used to compare the pre- and post-intervention differences between the control and intervention groups."

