The minimization algorithm will minimize the imbalance between groups, assigning more priority to variables 1 and 2. table 2 shows the values for the selected variables for all 24 pre-selected hospitals, and table 3 shows an example of one set of results of the minimization algorithm on these hospitals.

After the baseline data collection period the dataset will be analyzed by RTI. RTI will then apply the inclusion criteria to assess the eligibility of preselected hospital according to the baseline rate of episiotomy and active management. The statistician at CLAP will elaborate a computer program implementing the minimization algorithm. The source code of the algorithm will be made available in advance to RTI and UNC-CH for audit and testing. This computer program will be used by the statistician at RTI to allocate eligible hospitals to either intervention or control without participation of others. The assignment will then be communicated to CLAP. Thus, there will be a clear separation between the generator of the intervention assignment and the CLAP study coordination (Donner et al., 1998).

Table 2. Hospitals characteristics to be included in the minimization algorithm.

Hospital	Residents		Country		Size		Region	
	(1) Yes, (2) No		(1) Argentina, (2) Uruguay		(1) less than 2000, (2) 2000 or more		(1) Montevideo, (2) Salto/Paisandu, (3) Rosario, (4) Bs. Aires	
San Roque	Yes	1	Argentina	1	1500	1	Bs. Aires	4
M.V.de Martínez	Yes	1	Argentina	1	3400	2	Bs. Aires	4
Héroes de Malvinas	No	2	Argentina	1	3000	2	Bs. Aires	4
Materno Infantil	Yes	1	Argentina	1	2800	2	Bs. Aires	4
Bocalandro	No	2	Argentina	1	2200	2	Bs. Aires	4
Hosp. De Clínicas	Yes	1	Uruguay	2	1000	1	Mvdeo	1
Germani	No	2	Argentina	1	2500	2	Bs. Aires	4
Roque Saenz Peña	Yes	1	Argentina	1	1660	1	Rosario	3
Paroissien	Yes	1	Argentina	1	2800	2	Bs. Aires	4
Alejandro Korn	No	2	Argentina	1	1300	1	Bs. Aires	4
Durand	Yes	1	Argentina	1	2000	2	Bs. Aires	4
Ramon Carrillo	No	2	Argentina	1	1250	1	Bs. Aires	4
Hospital Centenario	Yes	1	Argentina	1	1300	1	Rosario	3
Equiza	No	2	Argentina	1	2800	2	Bs. Aires	4
Manuel Belgrano	Yes	1	Argentina	1	1200	1	Bs. Aires	4
San Martín	Yes	1	Argentina	1	3000	2	Bs. Aires	4
Hosp. Militar	Yes	1	Uruguay	2	1800	1	Mvdeo	1
Hospital de Paysandú	Yes	1	Uruguay	2	2100	2	Paysandú	2

---

Eva Perón	Yes	1	Argentina	1	1700	1	Rosario	3

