## ***5.2. Schedule of Data Collection***

Table 4 presents the components and the schedule for data collection in the project. There are three different sets of data to be collected, and the data collection system will be different for each one. These are

1. clinical outcomes,
2. readiness to change questionnaire to health providers, and
3. process measures.

Clinical outcomes and readiness to change questionnaire includes the primary and secondary outcomes of the project and will be measured in all participating hospitals (intervention and control arm). Process measures will be used to explore aspects of the intervention implementation, and they will be measured only in the intervention hospitals.

Clinical data will be collected in four periods, and each will be 1 year apart (Table 4):

- Period I. Baseline data collection: before randomization in the preparatory phase, for primary and secondary outcomes.
- Period II. Mid-intervention data collection: immediately before the implementation of the guidelines, for primary outcomes only.
- Period III. Main post-intervention data collection: immediately following the maintenance component of the intervention, for primary and secondary outcomes.
- Period IV. Second post-intervention data collection: 1 year after the main post-intervention data collection, for primary outcomes only.

Data from period I (baseline) and III will be used for the primary analyses, and include both primary and secondary outcomes. Secondary outcomes include nonroutine procedures to measure blood loss (see below). Data collection II will be used to study trends and will be limited to primary outcomes, which can be measured without interference with the clinical processes. Data collection IV will be used to measure the sustainability of the results after the end of the intervention and will also be limited to primary outcomes to avoid interference with the clinical processes.

**Table 4.** Schedule for data collection.

Project Stage	Year					hospitals	Forms	Tools for Data Entry & validation
	1	2	3	4	5			
	Preparatory Phase (Data Collection I - Baseline)	Intervention Phase (Data Collection II)	Maintenance Phase (Data Collection III and IV)	Analysis and writing- up				
Project clinical outcomes.								
Development and testing	■ ■ ■ ■ ■					24	Clinical Data Form (CLIN1, ALTA1, CLIN2, ALTA2)	Data Management Systems in hospitals
Training and implementation in Hospitals	■ ■ ■ ■ ■							
Data collection - Primary Outcomes		■ ■ ■ ■ ■						

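### Section 10.5 defends the t-test with a Normality argument that does not apply between hospitals, and names neither of its two t-tests as primary; baseline enters only through ratios and the minimisation factors not at all.

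*Protocol*

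**What the plan says.** Section 10.5 defines the group-level outcome by hospital: "the primary outcome variable is the percentage of primary and secondary outcomes during the three months following the end of the intervention". It accepts that there are only 12 values per arm, invokes the Normal approximation to the Binomial because births are many, and concludes "thus the individual percentages can be assumed to be Normally distributed". From this it infers that, "using the mean percentages at the end of the intervention period, the Student's t-test is appropriate and its use is justified".

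The same paragraph continues: "Baseline frequencies will also be presented, and baseline to follow-up ratios will be computed". Mantel-Haenszel summary risk ratios are then formed, and the arms are compared by a "t-test on the logarithms of the summary risk ratio". A further paragraph adds mixed models on individual data to explore confounding from imbalance, and GEE models across the four periods.

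Two other sections bear on this. Section 5.2 states: "Data from period I (baseline) and III will be used for the primary analyses". Section 3.4 allocates hospitals by minimisation on residents, country, size and region: "The minimization algorithm will minimize the imbalance between groups, assigning more priority to variables 1 and 2". Section 10 does not mention these four factors.

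**The concern.** A t-test on hospital percentages treats each hospital as one observation. What matters is the distribution of those observations across hospitals, that is, true between-hospital variation plus a smaller binomial part. Many births make each hospital's estimate of its own rate close to Normal; they do not make the rates Normal across hospitals, nor equally spread in the two arms. The protocol offers the first fact as proof of the second.

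The section also leaves open which group-level t-test carries the conclusion. The two answer different questions (a difference in follow-up percentages, and a ratio of changes from baseline) and can disagree. With at most 24 units and a baseline rate measured in every hospital, the choice also affects power.

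**Working it through.** **Inputs.** From section 10.3: episiotomy 40% to 20%; planned SD 15 points, observed SD 11; oxytocin baseline 10%, SD 5; 18 hospitals; alpha 0.05; power 80%. From section 10.5: 12 hospitals per arm. From section 3.2.1: at least 500 vaginal deliveries a year. From section 9.9.1: 3-month collection periods. Table 2 averages 47,760/24 = 1,990 deliveries a year. Assumed, because not stated: a two-sided test; 75% of deliveries vaginal; the baseline/follow-up correlation r.

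**1. The plan's own figure.** n per arm = 2(1.960 + 0.842)² × 15²/20² = 2 × 7.85 × 0.5625 = 8.8, so 9 per arm and 18 in all, as stated. This uses follow-up SDs only, with no baseline correlation. For the t-test itself (noncentral t, noncentrality 20/(15√(2/n))), power is 75.7% with 9 per arm and 87.7% with 12.

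**2. What the Binomial argument covers.** Binomial SE = √(p(1−p)/m); its share of the variance is SE²/SD².

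| Outcome | Births m | SE (points) | Share of variance |
|---|---|---|---|
| Episiotomy 40% | 125 (500/4) | 4.4 | 8.5% at SD 15; 16% at SD 11 |
| Episiotomy 40% | 373 (1,990/4 × 0.75) | 2.5 | 2.9% at SD 15; 5.3% at SD 11 |
| Oxytocin 10% | 125 | 2.7 | 29% at SD 5 |
| Oxytocin 10% | 373 | 1.6 | 10% at SD 5 |

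Most of the variation is outside the argument for both outcomes.

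**3. Does the error matter for type I error?** Simulated with 12 per arm, 250 births each and same-shaped arms, Student's test rejects in 5.0% (beta, mean 40%, SD 15), 4.9% (beta, 10%, SD 5), 5.2% (bimodal) and 3.1% (strongly skewed, mean 5%, SD 10) of runs. If the arms differ in spread (assumed SDs 5 and 20), the Student critical value is 2.07 against 2.17 for Welch; type I error is about 5.9% with Normal data, and 16% with bounded rates at a common mean of 10%. The last is a stress case.

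**4. Omitting the minimisation factors.** If one balanced two-level factor explains 10/20/30/50% of between-hospital variance (assumed), the unadjusted test with 12 per arm has type I error of about 4.0/2.8/1.9/0.5%. It is conservative.

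**5. Gain from baseline adjustment.** Episiotomy, 20 points, SD 15; simulated ANCOVA on Normal data, so that the cost of chance baseline imbalance is included:

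| Hospitals per arm | Unadjusted | r = 0.3 | r = 0.5 | r = 0.7 |
|---|---|---|---|---|
| 9 | 75.7% | 76% | 84% | 94% |
| 12 | 87.7% | 89% | 94% | 99% |

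Adding residents and country as covariates with no prognostic value gives, at r = 0.3, about 75% (9 per arm) and 88% (12 per arm).

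**6. Fixing the coefficient at 1.** A log ratio of follow-up to baseline is a change score on the log scale. The percentage-point analogue, with equal SDs at both periods, has SD 15√(2(1−r)) = 17.7, 15.0 and 11.6 for r = 0.3, 0.5 and 0.7. With 9 per arm its power is 61%, 76% and 93%. It beats ignoring baseline only when r exceeds 0.5.

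**The case against.** The strongest reply is that the plan already uses baseline and already considers imbalance. Section 10.5 has the ratio-based t-test, section 5.2 counts Period I among the data for the primary analyses, and mixed models are planned. This stands in part. A reader might infer that the plan discards the baseline rates and analyses follow-up percentages alone; the documents do not support that. What remains is that neither t-test is named primary, that the ratio imposes a coefficient instead of estimating it, and that the mixed models are exploratory and name no factor. The ratio test also has an unclear unit: a Mantel-Haenszel summary over a whole arm gives one value per arm, so a t-test needs one log ratio per hospital.

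A second reply is that the t-test is robust. That largely holds: with same-shaped arms the error rate is nominal or below. If the intervention changed no hospital's rate, the arms would share one distribution, so unequal spread mainly affects the interval once there is an effect.

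A third is that 12 per arm already gives 87.7% power and that the gain depends on an unknown correlation. This also stands. The entry limits on baseline rates and uneven adoption could both weaken that correlation.

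A fourth is that covariate lists and test variants belong in a statistical analysis plan, which is not shown. That would excuse silence. It does not excuse a stated justification that is wrong, or two competing tests in the protocol itself.

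**Conclusion.** The point holds in a limited form. The Normality justification does not follow and should not be the stated basis for the test. Two group-level t-tests stand side by side with no primary one, one blind to baseline and the other fixing its coefficient at 1, and neither reflects the minimisation.

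The consequence is lost efficiency and an undefined primary test. For episiotomy the gain from baseline adjustment runs from about 1 point or less at r = 0.3 to about 18 points (9 per arm) or 11 points (12 per arm) at r = 0.7. It rests on an assumed correlation, Normal data and the planned SD of 15. Little gain is expected for oxytocin, where the entry rule caps baseline at 15% and power is already high.

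A reader might also infer that the p-values are invalid, or that ignoring the restricted allocation inflates false positives. The checks do not support this: leaving out balanced factors makes the test conservative, and material inflation appeared only under an extreme assumed difference in spread.

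**What to change.** In section 10.5, delete the Normal-approximation justification. Name one primary hospital-level test per outcome: ANCOVA of the Period III percentage on arm and Period I percentage, adjusted for the two priority minimisation factors, residents and country. As support, give an unequal-variance (Welch) t-test or a re-randomisation test over the allocations that the minimisation program could have produced. If the ratio analysis is kept, label it secondary and define one log ratio per hospital.

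The cost is wording and a short program. No new data are needed, and section 3.4 already provides for the allocation code to be shared. The statistical price is up to three degrees of freedom (22 to 19 with 24 hospitals, 16 to 13 with 18), about 1 point of power with 9 per arm if the correlation is low and the factors are not prognostic.

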### ***10.3. Sample Size***

A preliminary analysis of 1995-98 PIS data from 22 Argentinean hospitals showed a baseline frequency of episiotomies among vaginal deliveries of 42%, with a standard deviation of 11%. To protect against changes in the standard deviation (Lomas et al., 1991), we have based our sample size calculations on a standard deviation of 15%. Thus, we will need 18 hospitals (9 intervention and 9 control) to identify a decrease of episiotomy rates from 40% to 20%, with a 0.05 significance level and a 80% power. Our previous analyses of PIS data have shown that about 25% of deliveries are among primiparae, and 75% among multiparae. A reduction of the general episiotomy rate from 40% to 20% could be achieved by reducing the rate among primiparae from 80% to 40%, and the rate among multiparae from 26% to 13%. The rates after the intervention would be similar to the rates achieved in a previous trial (Argentine Episiotomy Trial Collaboration Group, 1993) and are thus potentially attainable. However, the sample size of 18 hospitals will allow us to identify a smaller decrease of episiotomy rates among primiparae vaginal deliveries, from 80% to 60%, with a 0.05 significance level and a 80% power. Assuming a baseline frequency of perineal sutures among primiparae of 85% with a standard deviation of 15%, our sample size of 18 hospitals will give us a power of 80% to identify a reduction of frequency of perineal sutures to 65%, with a 0.05 significance level.

We expect the use of oxytocin during the third stage of labor to increase from 10% to 50%. However, our sample size will allow us to detect smaller changes. Assuming a baseline frequency of injections of oxytocin of 10% and a standard deviation of 5%, the sample size of 18 hospitals will give us a power higher than 95% to identify an increase of use of oxytocin from 10% to 20%, with a 0.05 significance level. Assuming a baseline PPH incidence rate of 15% and a standard deviation of 5%, the sample size of 18 hospitals will give us a power of

84% to identify a reduction from 15% to 8%, and a power of 56% if the reduction were from 15% to 10%.

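### Section 10.5 sets two between-arm tests for each primary outcome and does not say which decides, so the role of the baseline in the primary analysis is unsettled

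*Protocol*

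**What the plan says.** Section 10.5 takes each outcome's hospital percentage in the three months after the intervention as the primary outcome variable. It states that "when evaluating the efficacy of the intervention using the mean percentages at the end of the intervention period, the Student's t-test is appropriate". That is a comparison of Period III percentages without baseline.

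The paragraph goes on to baseline-to-follow-up ratios, combined by Mantel-Haenszel within each arm, and ends: "The intervention and non-intervention groups will then be compared at the group level using Student's t-test on the logarithms of the summary risk ratio". That is a second between-arm significance test on the same outcome, on the scale of relative change from baseline.

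The next paragraph gives the remaining methods limited roles: mixed models explore confounding and GEE studies the course over the four periods. Only the two t-tests therefore compete.

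Elsewhere in the protocol:
- Section 5.2: "Data from period I (baseline) and III will be used for the primary analyses, and include both primary and secondary outcomes".
- Section 5.5 places the assessment of outcome rates in Period III.
- Section 10.3 powers the trial, at 80%, on a difference in hospital percentages: "we will need 18 hospitals (9 intervention and 9 control) to identify a decrease of episiotomy rates from 40% to 20%, with a 0.05 significance".

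**The concern.** The two tests estimate different things. One is an absolute difference between arms at follow-up; the other is a difference in relative change that contains the baseline rate. Someone applying 10.5 as written would produce two p-values per primary outcome and would find no statement of which one answers the research question, or of what the trial concludes if they differ.

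Section 5.2 leaves the matter open, because it brings baseline data into the primary analyses without saying how. At stake are the meaning of the 0.05 level, which in 10.3 belongs to one comparison per outcome, and the protection against choosing the contrast after the results are seen. With at most 24 hospitals, a chance baseline difference between arms can move one test and not the other.

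**Working it through.** **1. Which comparison does 10.3 power?** Inputs from 10.3: difference 20 points, SD 15 points, level 0.05, power 80%.

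Hospitals per arm = 2(1.96 + 0.84)² × 15² / 20² = 8.8, rounded up to 9, as stated.

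Power at 9 per arm = Φ(δ / (σ√(2/9)) − 1.96):
- Episiotomy, 20 points, SD 15: 20/7.07 = 2.83, power 80.7% (stated 80%).
- Oxytocin, 10 points, SD 5: 10/2.36 = 4.24, power 98.9% (stated above 95%).
- Postpartum hemorrhage, 7 points, SD 5: power 84.4% (stated 84%).
- Postpartum hemorrhage, 5 points, SD 5: power 56.4% (stated 56%).

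All four reproduce as two-sided 0.05 comparisons of hospital percentages. The planning therefore fits the Period III t-test, with one test per outcome.

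**2. False-positive chance if either test could be claimed.** Let X and Y be a hospital's baseline and follow-up values, with equal variances and correlation ρ. Then

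corr(Y, Y − X) = (1 − ρ)/√(2(1 − ρ)) = √((1 − ρ)/2),

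and the chance that at least one of two two-sided 5% tests rejects under no effect is 1 − P(|Z₁| < 1.96 and |Z₂| < 1.96). The protocol does not give ρ, so a range is shown.

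| ρ | correlation of the tests | at least one rejects |
|---|---|---|
| 0.3 | 0.59 | 8.8% |
| 0.5 | 0.50 | 9.1% |
| 0.7 | 0.39 | 9.35% |
| 0.9 | 0.22 | 9.6% |

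Two independent tests would give 1 − 0.95² = 9.75%. The tests are moderately correlated at low ρ and weakly correlated only near ρ = 0.9.

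Simulations of hospital-level t-tests agree. They used 9 or 12 hospitals per arm, 400 or 500 assumed births per hospital and period, and t-tests on Period III percentages and on per-hospital log ratios. Each test alone rejects about 4–5% of the time, and at least one rejects about 8–10%. Oxytocin (10%, SD 5%) behaves in the same way.

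**3. How often would the verdicts differ?** This was simulated for episiotomy at a starting rate of 41%, between the 42% observed and the 40% planned in 10.3. The SD was 11% (observed) or 15% (planning value), with ρ from 0.3 to 0.9.

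| Fall from 41% to 20% | SD 11% | SD 15% |
|---|---|---|
| 12 per arm | about 1–2% | about 5–10% |
| 9 per arm | about 5–6% | about 14–18% |

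The 20% arm's SD was set to 12% for the SD 15% column. Using 12% in the SD 11% column as well gives 7–8% with 9 per arm.

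For a smaller fall, 41% to 30%, which is an assumed scenario, the verdicts differ in 24% to 58% of trials. For oxytocin at the expected rise from 10% to 50%, with an assumed follow-up SD of 15%, they differ in under 1%.

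**4. Does a baseline-adjusted comparison serve as a single test?** Under no effect it rejects in 4.6–5.1%. For the assumed fall from 41% to 30%, SD 15%, 12 per arm, its power is 41–94% as ρ runs from 0.3 to 0.9, against 39–41% for the Period III t-test.

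**The case against.** The best counter-argument is that the protocol leans clearly one way. Section 10.5 names the Period III percentage as the outcome variable, 5.5 assesses outcomes in Period III, and 10.3 powers that contrast. The ratio comparison follows a sentence about also presenting baseline frequencies, so it can be read as secondary. This stands as far as it goes. It makes the repair easy, but it does not label the ratio test, which 10.5 says will be carried out.

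A reader might infer that 5.2 contradicts the Period III test and fits only the ratio test. The text does not support that. Section 5.2 allots data-collection periods to uses and names no test, and 10.5 also presents baseline frequencies and explores imbalance. What remains is that the role of the baseline is unspecified.

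A reader might also infer that the trial's error rate is 9%. Nothing in the protocol says that significance on either test counts as success, and each test alone holds about 5%. Nor is disagreement common at the effects the trial plans for, particularly with 12 hospitals per arm.

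Finally, ranking analyses is often left to a statistical analysis plan, and one may exist. That would excuse silence. Here the protocol itself commits to two tests and assigns data to the primary analyses, so its own statements need reconciling.

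**Conclusion.** The point holds as an unranked pair of tests, with the Period III comparison better supported by the text and the baseline's role left open. It is not a demonstrated inflation of the error rate.

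If significance on either test were claimed, the false-positive chance for one outcome would be roughly 8–10% against the stated 5%. That rests on three things: an either-test rule the protocol does not state; a baseline to follow-up correlation of 0.3–0.9 that it does not give; and per-hospital log ratios standing in for the Mantel-Haenszel summary ratio, which read literally is one number per arm. The figure does not include the effect of having two primary outcomes.

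Conflicting verdicts are rare to moderately frequent at the planned effect and more frequent at smaller, assumed effects. The ambiguity should be removed before any outcome comparison is seen.

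**What to change.** In 10.5, state that for each primary outcome the deciding comparison is the between-arm difference in hospital Period III percentages, adjusted for the hospital's Period I percentage, at two-sided 0.05. State that the unadjusted t-test, the baseline-to-follow-up ratio comparison and the mixed models are supportive and will not change the conclusion. In 5.2, say that Period III supplies the outcome and Period I the adjustment.

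This keeps the percentage scale of the 10.3 calculation and uses baseline data already collected. Naming the unadjusted Period III t-test instead would also remove the ambiguity, but it would leave the baseline unused in the deciding comparison.

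The cost is two sentences in 10.5 and one in 5.2, with no new data or hospitals. The adjustment uses one degree of freedom (22 to 21 with 12 per arm, 16 to 15 with 9). A positive ratio test alone could no longer be presented as the primary result.

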## ***2.2. Primary Hypotheses***

Our main hypothesis is that an intervention designed to motivate and facilitate health care professionals' development through the implementation and maintenance of simple evidence-based guidelines can increase the use of evidence-based practices by birth attendants at the hospital level in Argentina and Uruguay.

The main specific aim of this project is to perform a randomized controlled trial of a behavioral intervention intended to increase the use of two evidence-based birth practices, the selective use of episiotomies and active management of the third stage of labor (injection 10 IU of oxytocin). We will randomize 24 hospitals in Department of Montevideo, Uruguay, the Province of Buenos Aires, Argentina, and the City of Rosario, Argentina.

The *main research questions* to test the main hypothesis are the following:

- Does the proposed intervention decrease the frequency of episiotomies (primary outcome) and of perineal sutures (secondary outcome) in the intervention hospitals relative to the control hospitals?
- Does the proposed intervention increase the frequency of injections of oxytocin during the third stage of labor (primary outcome), and decrease the frequency of postpartum hemorrhages (secondary outcome) in the intervention hospitals relative to the control hospitals?

*Secondary research questions* are the following:

- Does the proposed intervention increase the readiness to change of birth attendants (secondary outcome) in the intervention hospitals relative to the control hospitals?
- Are the effects, if any, sustained 1 year after the end of the intervention?

Our *other aims* are to do the following:

Facilitate capacity building within the Latin American Center for Perinatology (CLAP: Centro Latinoamericano de Perinatología) and among its network of hospitals, so that they may increase their ability to perform studies integrating behavioral and clinical research methods, and to perform large scale studies using state-of-the-art information technology.

Contribute to the Global Network by increasing access to a large number of Latin American hospitals that have the capacity to participate in multicentric randomized controlled trials and other clinical studies.

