### ***3.4. Randomization Procedures***

Preselected hospitals will perform a baseline data collection. According to the results of the analysis of the baseline data collection, hospitals will be excluded from the study if the episiotomy rate in primiparous women is below 70% or the rate of active management is higher than 15% (see section 3.2). Those hospitals fulfilling the inclusion criteria will be randomized to either the intervention or the control group.

This study has a maximum of only 24 hospitals to allocate to the control or intervention group, and random allocation may not provide adequate balance in the groups (Treasure and MacRae, 1998). In addition, stratified allocation may not be feasible due to there being too few numbers to stratify by all important variables (Treasure and MacRae, 1999).

Minimization has the particular advantage that it can make small groups of units closely similar with respect to several unit characteristics (Altman et al., 2001). A randomization lists is not set up in advance. The first unit is truly randomized, but in each subsequent unit the treatment allocation is identified which would minimize the imbalance between groups (Pocock, 1983). In this trial all units (hospitals) enters the study at the same time, and all prognostic variable are known in advance. In this situation a computer algorithm can choose by random one allocation sequence among a set of sequences that minimizes the imbalance between groups. Such algorithm will be used to allocate hospitals in this study.

Minimization offers an acceptable alternative to randomization, and some have argued that it is superior. (Treasure and MacRae, 1998). Trials that use minimization are considered methodologically equivalent to randomized trials according to the Consort

Statement (Moher et al., 2001), endorsed by the BMJ, JAMA, Annals of Internal Medicine and The Lancet, among others.

There are four hospital characteristics that were selected as important prognostic variables. These are the variables that will be included in the minimization algorithm to assure balance between groups.

1. Teaching hospital with residents (Yes-No).
2. Country (Argentina-Uruguay).
3. Hospital size (less than 2000 – 2000 or more deliveries per year).
4. Region (Montevideo, Salto/Paisandu, Rosario, Buenos Aires).

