### ***10.2. Design Issues***

Episiotomy rate and active management rate will be assessed before randomization (baseline) and at the end of the intervention period in all hospitals (Table 4). As a subgroup analyses, the effect of the intervention on episiotomy rate will be assessed on primiparous women. Episiotomy and active management rates will be also measured 1 year after the end of the intervention period to assess the maintenance of the effect of the intervention.

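### For persistence at one year, the only inferential method section 10.5 names is GEE on at most 24 hospitals; with the usual variance and normal reference its 5% test errs about 7-10% of the time

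*Protocol*

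**What the plan says.** Protocol section 2.2 lists this as a secondary research question: "Are the effects, if any, sustained 1 year after the end of the intervention". Section 5.2 assigns the data: "Data collection IV will be used to measure the sustainability of the results after the end of the intervention". Section 10.2 says that both primary rates are also "measured 1 year after the end of the intervention period to assess the maintenance of the effect of the intervention".

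Section 10.5 names three model-based approaches for the clinical outcomes and gives each its own job:

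- The Student's t-test, on rates or on log summary risk ratios, applies to "the percentage of primary and secondary outcomes during the three months following the end of the intervention". By sections 5.2 and 5.5 this is Period III.
- The mixed models use individual data "to explore the potential for confounding of the main effects of the intervention due to imbalances arising from the group randomization".
- For the time course, "we will use descriptive statistics and GEE modeling" "to study the evolution of frequencies of outcomes between the four data collection periods".

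On the number of clusters, section 3.4 states: "This study has a maximum of only 24 hospitals to allocate to the control or intervention group". Section 10.3 sizes the trial on 18 hospitals, 9 per arm. Section 10.1 directs inference primarily at the hospital level.

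**The concern.** Set side by side, these sections leave GEE as the only inferential method named for Period IV, and so for a stated research question. The usual GEE (sandwich) variance is justified for a large number of clusters. With 18 to 24 hospitals it tends to be too small, and a normal reference ignores how imprecisely it is estimated. Section 10.5 recognises that 12 observations per arm are few and argues why a t-test is acceptable at Period III. It gives no such argument for GEE.

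What is at stake is the claim that practice change persisted, or faded, after support ended. Confidence intervals that are too narrow would make either claim too easily. The primary Period III result is not at stake.

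**Working it through.** **1. The plan's own figure.** Inputs from section 10.3: episiotomy 40% to 20%, between-hospital SD 15%, significance level 0.05 (taken as two-sided), power 80%.

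- n per arm = 2 × (1.960 + 0.842)² × 0.15² / 0.20² = 8.8, so 9 per arm and 18 hospitals.
- Power at 9 per arm: 0.20 / (0.15 × √(2/9)) = 2.83; 2.83 − 1.96 = 0.87; power 80.7%.

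This reproduces the stated 18. The same formula gives 84.4% and 56.4% for the two hemorrhage cases (stated 84% and 56%) and 98.9% for oxytocin (stated above 95%).

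**2. Simulation under no effect.**

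- From the protocol: 24 or 18 hospitals; rates and SDs of 40% / 15% and 10% / 5% (section 10.3); annual deliveries per hospital from Table 2 (mean 1,990); 3-month collection periods (section 9.9.1).
- Assumed: 75% of deliveries vaginal, so on average 1,990 × 0.75 / 4 ≈ 373 births per hospital per period; between-period correlation 0.5; beta-distributed hospital rates.

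**3. Logistic GEE, independence working correlation.** With P = Σy/N the pooled rate in an arm, where N = Σn, the arm effect is the difference in log{P/(1 − P)}. Its sandwich variance is the sum over hospitals of [(y − nP) / (N·P(1 − P))]². For the change from Period I to IV, each hospital's two residual terms are differenced before squaring. The Mancl-DeRouen correction divides each hospital's term by (1 − n/N).

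Rejection rates at nominal 5%, 10,000 runs per row (Monte Carlo SE near 5% is √(0.05 × 0.95 / 10,000) = 0.2 points):

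| Hospitals | Rate / SD | Sizes | Usual GEE, Period IV level | Usual GEE, change I-IV | Corrected GEE with t, level | Hospital t-test, level | Hospital t-test, change |
|---|---|---|---|---|---|---|---|
| 24 | 40 / 15 | Table 2 | 8.5% | 8.9% | 4.5% | 5.2% | 5.3% |
| 24 | 10 / 5 | Table 2 | 8.9% | 9.4% | 4.9% | 5.0% | 5.1% |
| 24 | 40 / 15 | equal | 7.1% | 7.1% | 3.8% | 5.0% | 4.9% |
| 18 | 40 / 15 | Table 2 | 8.9% | 9.2% | 4.0% | 5.0% | 5.1% |
| 18 | 10 / 5 | Table 2 | 10.0% | 10.0% | 4.4% | 4.9% | 5.0% |
| 18 | 40 / 15 | equal | 9.0% | 8.9% | 4.1% | 5.6% | 5.2% |

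Here usual GEE means the uncorrected sandwich variance with the normal reference. Corrected GEE uses Mancl-DeRouen with t on 24 − 2 = 22 or 18 − 2 = 16 degrees of freedom.

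- The uncorrected standard error averages 3-8% too small with 24 hospitals and 6-9% too small with 18.
- Changing only the reference to t, without correcting the variance, leaves 5.8-7.5% with 24 hospitals and 6.7-7.6% with 18. Both changes are therefore needed.

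**4. Four-period GEE, exchangeable correlation.** This is fitted to hospital-period rates and is closest to the wording of section 10.5. For the arm-by-Period IV term (about 14,000 runs per cluster count), the usual form gives 7.3% with 24 hospitals and 8.5% with 18. With the Mancl-DeRouen variance and the normal reference these become 5.0% and 5.5%.

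**5. Sensitivity.** A separate independence-GEE simulation, with correlation 0.6 and 250-700 births per hospital, gave 8-9% with 24 hospitals and 9-10% with 18. The hospital-level t-test gave 4.6-5.0% on the same data.

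**The case against.** The strongest objection is that the protocol names GEE and nothing more: no link, working correlation, variance estimator or reference distribution. A corrected GEE with a t reference complies fully with section 10.5 and holds its level. Such details normally belong in the statistical analysis plan, which was not available. This stands. A reader might infer that the protocol prescribes uncorrected standard errors, or that its intervals will be too narrow. The text supports neither, so every error rate for the usual form is conditional on that form being used. What remains is that the protocol itself chose the method for Period IV, and the standard form of that method performs poorly at this number of clusters.

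Three further points are fair:

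- The same sentence also names descriptive statistics, so GEE is the only method named for inference, not the only method named.
- The GEE role is supportive, and section 10.3 sets no power target for Period IV. Even so, sections 2.2, 5.2 and 10.2 make persistence a question the trial means to answer.
- A planned-size effect that persists would survive. With 20 points, SD 15 and 12 per arm, the SE is 15 × √(2/12) = 6.1 and the ratio is 20 / 6.1 = 3.3. An 8% error in the SE would not change that conclusion. The problem concerns small or borderline Period IV differences.

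**Conclusion.** The point holds in conditional form. If the GEE is run with the usual sandwich variance and a normal reference, a nominal 5% test has a type I error of about 7-9% with 24 hospitals and 8.5-10% with 18. Put as coverage, nominal 95% intervals would cover about 91-93% and 90-91.5% of the time under no effect. The exact figures rest on the assumed vaginal-delivery share, births per hospital, between-period correlation and distribution of hospital rates. The direction was the same in every setting tried, including equal hospital sizes.

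The inflation is moderate and confined to the four-period and one-year analyses. It would be wrong to read it as a weakness of the primary result, which rests on a hospital-level t-test at Period III. That type of test stayed at 4.9-5.6% in the main set of simulations. This is a cheap improvement, not an error that undermines the trial.

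**What to change.** Add one sentence to section 10.5 or to the statistical analysis plan. It should say that the arms are compared at Period IV with the same hospital-level t-test as at Period III, on hospital rates or on hospital changes. This follows the hospital-level inference already stated in section 10.1.

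If GEE is kept for trends across the four periods, specify a bias-corrected sandwich variance (for example Mancl-DeRouen) and a t reference on hospitals minus 2 degrees of freedom.

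No new data or design change is needed. The cost is somewhat wider intervals. For GEE with 24 hospitals, undoing a 3-8% shortfall multiplies the SE by 1/0.97 = 1.03 to 1/0.92 = 1.09. The t multiplier adds 2.07/1.96 = 1.06. Intervals would be roughly 9-15% wider, if the correction restores the SE to its true size.
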